#### 9.4.4 SAFETY ANALYSES

Rates of adverse events including, nausea, vomiting, indigestion, worsening of shortness of breath or difficulty breathing, allergic reaction (skin rash, hives, swelling of lips or tongue), and hospitalized or physician visit will be included in secondary analysis as outlined in **Section 9.4.3**. Unsolicited adverse events recorded will be categorized as “other adverse events” and will be described as a incidence rate expressed as a percentage. Each adverse event recorded will be only counted once for any given study subject during the study follow-up period. The 10th revision of the International Statistical Classification of Diseases and Related Health Problems (ICD-10) codes will be used to code adverse events where appropriate. Severity of adverse events will be classified as follows:

- **MILD:** Awareness of signs or symptoms, but easily tolerated and are of minor irritant type causing no loss of time from normal activities. Symptoms do not require therapy or a medical evaluation; signs and symptoms are transient.
- **MODERATE:** Events introduce a low level of inconvenience or concern to the participant and may interfere with daily activities, but are usually improved by simple therapeutic measures; moderate experiences may cause some interference with functioning
- **SEVERE:** Events interrupt the participant's normal daily activities and generally require systemic drug therapy or other treatment; they are usually incapacitating

Expectedness of adverse events will be determined as follows:

- **UNEXPECTED** - nature or severity of the event is not consistent with information about the condition under study or intervention in the protocol, consent form, product brochure, or investigator brochure.
- **EXPECTED** - event is known to be associated with the intervention or condition under study.

Relatedness of adverse events will be determined as follows:

- DEFINITELY RELATED: The adverse event is clearly related to the investigational agent/procedure – i.e. an event that follows a reasonable temporal sequence from administration of the study intervention, follows a known or expected response pattern to the suspected intervention, that is confirmed by improvement on stopping and reappearance of the event on repeated exposure and that could not be reasonably explained by the known characteristics of the subject's clinical state.
- POSSIBLY RELATED: An adverse event that follows a reasonable temporal sequence from administration of the study intervention follows a known or expected response pattern to the suspected intervention, but that could readily have been produced by a number of other factors.
- NOT RELATED: The adverse event is clearly not related to the investigational agent/procedure - i.e. another cause of the event is most plausible; and/or a clinically plausible temporal sequence is inconsistent with the onset of the event and the study intervention and/or a causal relationship is considered biologically implausible.

Dates of adverse events self-reported by study participants will be recorded, and any adverse event leading to premature discontinuation from the study including serious treatment-emergent AEs will be listed.

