#### 4.3 JUSTIFICATION FOR DOSE

##### Zinc Citrate

Zinc is an essential trace element with a wide therapeutic index, and deficiency is common in developing nations and in the elderly (normal range: 10 - 16.8  $\mu$ M). Zinc deficiency has been associated with

increased pneumonia risk, and supplemental doses greater than 75 mg/day have been associated with a reduction in the duration of the common cold. A total daily dose of elemental zinc up to 207mg given for seven days has been studied in adults with common cold, and doses ranging between 100 to 150 mg/day have been administered for months at a time for other indications with few adverse effects reported. A recent study specifically evaluating zinc lozenges (78mg elemental zinc/day) administered for five days for common cold reported side effects of taste disturbances (52%) and dry or sore mouth (24%) that occurred at a greater rate than placebo (7% and 2%, respectively). However, no serious events were reported.

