### 8.3.4 TIME PERIOD AND FREQUENCY FOR EVENT ASSESSMENT AND FOLLOW-UP

The occurrence of an adverse event (AE) or serious adverse event (SAE) may come to the attention of study personnel during study visits and interviews of a study participant presenting for medical care, or upon review by a study monitor.

All AEs including local and systemic reactions not meeting the criteria for SAEs will be captured on the appropriate case report form (CRF). Information to be collected includes event description, time of onset, relationship to study product (assessed only by those with the training and authority to make a diagnosis), and time of resolution/stabilization of the event. All AEs occurring while on study must be documented appropriately regardless of relationship. All AEs will be followed to adequate resolution.

Any medical condition that is present at the time that the participant is screened will be considered as baseline and not reported as an AE. However, if the study participant's condition deteriorates at any time during the study, it will be recorded as an AE.

Study research technicians will record all reportable events via daily telephone visits with start dates occurring sometime near 24 hours after informed consent is obtained and continue until 2 days (for non-serious AEs and SAEs) after the last planned day of study drug administration (total of 7 days). At each study visit, study research technicians will inquire about the occurrence of AE/SAEs since the last visit. Events will be followed for outcome information until resolution or stabilization.

Solicited events will include patient self-reported:

- Nausea
- Vomiting
- Indigestion
- Worsening of shortness of breath or difficulty breathing
- Allergic reaction
  - skin rash
  - hives
  - swelling of lips or tongue
- Hospitalized or physician visit for study drug related adverse effect

Unsolicited events will include any patient self-reported adverse event that is provided without prompting by the research technician and that is not related/similar to any of the solicited events being collected.

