#### 9.4.3 ANALYSIS OF THE SECONDARY ENDPOINT(S)

Secondary endpoints are independent of findings from the primary endpoint.

Rates of adverse events will be determined as a percentage of those subjects self-reporting an event compared to the total cohort following seven days of follow-up. Adverse events will be categorically expressed as a single endpoint. Difference in adverse events will be compared using Chi-squared test with incidence rates expressed as percentages. Analysis will be performed based on intention-to-treat. Missing data will be handled by last observation carried forward based on most recent self-reported adverse event (or lack thereof).

Rates of missed days of work or school will be determined as a percentage of those subjects self-reporting a missed day compared to the total cohort following seven days of follow-up. Missed days will be both categorically expressed as a single endpoint with incidence rates expressed as percentages as well as mean days missed with standard deviation. Difference in missed days will be compared using Chi-squared test for categorically expressed missed days (occurrence of any missed day(s) during study follow-up) and student's t-test for mean days missed. Analysis will be performed based on intention-to-treat. Missing data will be handled by last observation carried forward based on most recent self-reported missed day (or lack thereof).

Rates of seeking medical care including physician office visits or hospitalization for worsening respiratory illness will be determined as a percentage of those subjects self-reporting these events compared to the total cohort following seven days of follow-up. A physician office visit or hospitalization for worsening respiratory illness will be categorically expressed as a single endpoint with incidence rates expressed as percentages. Difference in need to seek medical care will be compared using Chi-squared tests. Analysis will be performed based on intention-to-treat. Missing data will be handled by last observation carried forward based on most recent self-reported medical visit (or lack thereof).

---

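### Unsolicited adverse events are reported as one pooled percentage; no summary by event type and arm is planned, and it is unclear whether they enter the compared adverse-event endpoint

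*Combined protocol and SAP*

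**What the plan says.** Section 9.4.4 treats the two kinds of adverse event differently. The solicited checklist (nausea, vomiting, indigestion, worse breathing, allergic reaction, and a hospital or physician visit) "will be included in secondary analysis as outlined in" Section 9.4.3. For everything else the rule is "Unsolicited adverse events recorded will be categorized as" other adverse events, a single group that "will be described as a incidence rate expressed as a percentage". The sentence mentions neither event type nor treatment arm. The same section says ICD-10 "codes will be used to code adverse events where appropriate", counts each event once per participant, and defines grades for severity, expectedness and relatedness. It names no table that uses the codes or the grades.

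Section 9.4.3 gives the comparative analysis: "Adverse events will be categorically expressed as a single endpoint", tested by chi-square. It does not say whether unsolicited events count toward that endpoint.

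Section 8.3.4 defines unsolicited events as those the participant volunteers, unlike the checklist items. It has every event recorded with its description, onset, relationship to study product and resolution.

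**The concern.** The first secondary objective (Sections 1.1 and 3) is to compare adverse events between the combination and placebo. Section 2.3.3 says the combination has not been evaluated in this way before, so its harms need not fall on a short checklist. Section 4.3 itself mentions effects the checklist omits. For zinc lozenges it cites "side effects of taste disturbances (52%) and dry or sore mouth (24%) that occurred at a greater rate than placebo" (7% and 2% on placebo), and for vitamin C above 2000 mg/day it cites diarrhea. If such effects were volunteered in this trial, they would go into the pooled group.

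A pooled percentage mixes an arm-specific effect with unrelated complaints common to both arms. The difference shrinks, its standard error usually grows, and the reader cannot see which event caused it. If 9.4.3 is meant to include unsolicited events, the mixing goes further, because the checklist items join the same yes/no endpoint. On either reading no result by type and arm is planned.

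**Working it through.** **The plan's own figure.** The documents give no rate, precision or power for unsolicited events. Section 9.2 limits its power calculation to the primary endpoint. Its formula, with 1.96 and 0.84 for 60% v 30%, gives 41.92, so 42 per arm and 84 in total, as stated. That figure is not in dispute. The only input used below is the target of 50 per arm (Section 9.2).

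**Is a summary by type and arm promised elsewhere?**
- 9.4.4: codes and grades are assigned, but no table uses them. Only events leading to discontinuation, including serious ones, are listed.
- 9.4.3: one yes/no adverse-event endpoint, not split by type.
- 9.4.8: participant data tabulated by measure and time point, not by event type.
- 8.3.5: the overall rate of solicited and unsolicited events is monitored.
- 10.1.6: the safety monitor reviews data on each arm. This is oversight during the trial, not a planned trial result.

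None of these supplies the missing summary.

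**Size of the dilution (all rates assumed).** Let an unlisted effect occur in h = 12% on active and 2% on placebo. Let independent background complaints occur in a proportion b of both arms.

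Pooled proportion = 1 − (1 − b)(1 − h), so the pooled difference = (1 − b) × (0.12 − 0.02).

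z = difference / √(p₁q₁/50 + p₂q₂/50).

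| Background b | Active | Placebo | Difference (points) | Risk ratio | z |
|---|---|---|---|---|---|
| None (own row) | 12.0% | 2.0% | 10 | 6.0 | 2.0 |
| 30% | 38.4% | 31.4% | 7 | 1.22 | 0.7 |
| 40% | 47.2% | 41.2% | 6 | 1.15 | 0.6 |
| 60% | 64.8% | 60.8% | 4 | 1.07 | 0.4 |

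For b = 30%: 1 − 0.70 × 0.88 = 0.384 and 1 − 0.70 × 0.98 = 0.314. The standard error rises from √(0.12×0.88/50 + 0.02×0.98/50) = 5.0 points in the own row to √(0.384×0.616/50 + 0.314×0.686/50) = 9.5 points pooled.

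**Would the own row reach significance?** Not reliably. The expected split is 6/50 v 1/50. Pearson chi-square = 100 × (6×49 − 44×1)² / (50 × 50 × 7 × 93) = 3.840, p = 0.05004, just above 0.05. Fisher's exact p = 0.11.

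**Second set of assumptions.** Exact chi-square power at 50 per arm for 10% v 0% is 75% in its own row. Pooled with a background of 10% to 40% it falls to 26% to 10%. By-type power is only 38% for 10% v 2% and 15% for 5% v 1%.

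**What a by-type row can show.** The chance of at least one case among 50 on active is 1 − (1 − p)⁵⁰: 39%, 64%, 92% and 99% for true incidences of 1%, 2%, 5% and 10%.

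**The case against.** The strongest reply is that nothing is lost. Each event is described, coded where appropriate and graded, so a table by type could be made at any time. Serious events are reported (8.3.6), and events leading to discontinuation are listed (9.4.4). The safety monitor sees safety data by arm at 25%, 50%, 75% and 100% of enrollment. Section 9.4.3 does not restrict its comparison to solicited events. All of this stands, and it rules out some stronger readings.

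- A reader might infer that the trial cannot identify any harm outside the checklist. The listing and reporting of serious events and discontinuations contradict that.
- A reader might infer that unsolicited events are never compared between arms. The plan is silent on this; it does not exclude a comparison.
- A reader might infer that the pool would consist mostly of the presenting illness, because 8.3.4 says that if a participant's "condition deteriorates at any time during the study, it will be recorded as an AE". No section supports that. The 12 symptoms are asked about at every call (8.1), whereas unsolicited events are volunteered. Where worsening found by questioning is filed is at most ambiguous.

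It is also fair that the examples are indirect. The taste and mouth effects come from lozenges, while this trial uses swallowed capsules. Diarrhea is cited for vitamin C above 2000 mg/day, against 400 mg/day here. They show what the checklist omits; they do not predict rates in this trial.

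The reply does not supply the missing commitment. A table that could be made is not a planned one, and the sentence as written asks for a single percentage.

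**Conclusion.** The concern holds in a limited form. The plan collects and codes unsolicited events but commits only to one pooled percentage, and it leaves the scope of the 9.4.3 endpoint open. The exposure is confined to non-serious, off-checklist events that do not lead to discontinuation. For those, the pooled difference equals the true difference multiplied by (1 − b): 10 points becomes 7, 6 or 4 for backgrounds of 30%, 40% or 60%. These figures rest on assumed rates and on independence of effect and background, so they illustrate the mechanism and are not estimates for this trial.

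Nor should a reader infer that a by-type table would give reliable detection. At 50 per arm its power is low for modest differences, and even 12% v 2% narrowly misses p < 0.05 on the plan's chi-square. Its value is descriptive: it shows which events occurred, how often, and in which arm. The primary analysis is unaffected.

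**What to change.** In 9.4.4, replace the sentence on unsolicited events with: *Unsolicited adverse events will be tabulated by ICD-10 coded term or category and by arm (participants with at least one event, n and %, risk difference with 95% CI, descriptive only), with any other adverse event kept as a total line.*

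In 9.4.3, state whether the compared adverse-event endpoint covers solicited events only or all adverse events.

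Leave the recording rule in 8.3.4 unchanged. Dropping worsening symptoms from adverse-event capture to tidy the pooled percentage would conflict with that section's requirement to document every event regardless of relationship.

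The cost is one more safety table, built from data already collected and from coding already planned. Its rows will have small counts and wide intervals, so it should be read descriptively and without formal testing.

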#### 9.4.5 BASELINE DESCRIPTIVE STATISTICS

Baseline characteristics planned to be collected include the following:

- age
- sex
- height
- weight
- ethnicity
- history of asthma
- history of chronic obstructive pulmonary disease (COPD)
- history of diabetes
- COVID-19 status
- history of hospitalization for respiratory condition within the past year

#### 9.4.6 PLANNED INTERIM ANALYSES

N/A

#### 9.4.7 SUB-GROUP ANALYSES

Sub-group analysis based on patient demographic variables (e.g. age, sex, race/ethnicity) will not be performed.

#### 9.4.8 TABULATION OF INDIVIDUAL PARTICIPANT DATA

Study subject data will be tabulated by measure and time point through the study follow-up period.

#### 9.4.9 EXPLORATORY ANALYSES

The impact of combination supplementation against placebo on symptom duration and severity in the COVID-19 positive subgroup of enrolled patients will be assessed as an exploratory endpoint. This outcome will be determined from observing the proportion of COVID-19 positive patients (expressed as percentage) recovered from cold and flu-like symptoms (defined as scoring 0 or 1 daily total symptom severity score) following seven days of follow-up. Recovery from cold and flu-like symptoms will be categorically assessed as a single endpoint. The difference in recovery rates between study drug and placebo will be compared using Chi-squared test and be expressed with 95% confidence intervals. Analysis will be performed based on intention-to-treat. Missing data will be handled by last observation carried forward based on most recent self-reported total daily symptom severity score.

### 10 SUPPORTING DOCUMENTATION AND OPERATIONAL CONSIDERATIONS

#### 10.1 REGULATORY, ETHICAL, AND STUDY OVERSIGHT CONSIDERATIONS

##### 10.1.1 INFORMED CONSENT PROCESS

###### 10.1.1.1 CONSENT/ASSENT AND OTHER INFORMATIONAL DOCUMENTS PROVIDED TO PARTICIPANTS

Consent forms describing in detail the study intervention, study procedures, and risks are given to the participant and written documentation of informed consent is required prior to starting intervention/administering study intervention. The following consent materials are provided separately from this protocol:

Consent for randomized control trial  
Consent for separate blood sample study

###### 10.1.1.2 CONSENT PROCEDURES AND DOCUMENTATION

Informed consent is a process that is initiated prior to the individual's agreeing to participate in the study and continues throughout the individual's study participation. Consent forms will be Institutional Review Board (IRB)-approved and the participant will be asked to read and review the document. The investigator will explain the research study to the participant and answer any questions that may arise. A verbal explanation will be provided in terms suited to the participant's comprehension of the purposes, procedures, and potential risks of the study and of their rights as research participants. Participants will have the opportunity to carefully review the written consent form and ask questions prior to signing. The participants should have the opportunity to discuss the study with their family or surrogates or think about it prior to agreeing to participate. The participant will sign the informed consent document prior to any procedures being done specifically for the study. Participants must be

informed that participation is voluntary and that they may withdraw from the study at any time, without prejudice. A copy of the informed consent document will be given to the participants for their records. The informed consent process will be conducted and documented in the source document (including the date), and the form signed, before the participant undergoes any study-specific procedures. The rights and welfare of the participants will be protected by emphasizing to them that the quality of their medical care will not be adversely affected if they decline to participate in this study. Non-English-speaking patients will be offered language interpreting services for purposes of consenting. Patients not able to make sound decisions for themselves will not be approached for consent and study enrollment.

#### 10.1.2 STUDY DISCONTINUATION AND CLOSURE

This study may be temporarily suspended or prematurely terminated if there is sufficient reasonable cause. Written notification, documenting the reason for study suspension or termination, will be provided by the suspending or terminating party to study participants, investigators, and regulatory authorities. If the study is prematurely terminated or suspended, the Principal Investigator (PI) will promptly inform study participants, the Institutional Review Board (IRB), and Independent Safety Monitor and will provide the reason(s) for the termination or suspension. Study participants will be contacted, as applicable, and be informed of changes to study visit schedule.

Circumstances that may warrant termination or suspension include, but are not limited to:

- Determination of unexpected, significant, or unacceptable risk to participants
- Insufficient compliance to protocol requirements
- Data that are not sufficiently complete and/or evaluable
- Determination of futility

Study may resume once concerns about safety, protocol compliance, and data quality are addressed, and satisfy the IRB and/or Food and Drug Administration (FDA).

#### 10.1.3 CONFIDENTIALITY AND PRIVACY

Participant confidentiality and privacy is strictly held in trust by the participating investigators and their staff. This confidentiality is extended to cover testing of biological samples and genetic tests in addition to the clinical information relating to participants. Therefore, the study protocol, documentation, data, and all other information generated will be held in strict confidence. No information concerning the study or the data will be released to any unauthorized third party without prior written approval of the primary investigator.

All research activities will be conducted in as private a setting as possible.

The study monitor, other authorized representatives of the primary investigator, representatives of the Institutional Review Board (IRB), and regulatory agencies may inspect all documents and records required to be maintained by the investigator, including but not limited to, medical records (office, clinic, or hospital) and pharmacy records for the participants in this study. The clinical study site will permit access to such records.

The study participant's contact information will be securely stored at each clinical site for internal use during the study. At the end of the study, all records will continue to be kept in a secure location for as long a period as dictated by the reviewing IRB and Institutional policies.

Study participant research data, which is for purposes of statistical analysis and scientific reporting, will be transmitted to and stored at University of Missouri Health Care. This will not include the participant's contact or identifying information. Rather, individual participants and their research data will be identified by a unique study identification number. Given the ubiquitous nature of cold and flu-like illness, including COVID-19, deidentified information including patient demographic data such as age, ethnicity, sex, etc. is not expected to make any individual or group of individuals identifiable. The key for identifying patients with their unique study number will be kept with the Investigational Drug Service (IDS) pharmacist for the duration of the study period, and it will be stored under lock and key in the IDS pharmacy or password protected in a dedicated IDS database folder located at University of Missouri Health Care for digital storage. The study data entry and study management systems used by clinical sites and by University of Missouri Health Care research staff will be secured and password protected. Sharing unidentified data will occur as necessary amongst research team members as well as the study monitor for such reasons as to review adverse events including assessment of severity, expectedness, and relatedness. At the end of the study, all study databases will be de-identified and archived at University of Missouri Health Care.

